6.3 Treatment supply, labelling, storage, accountability, and disposal

The project coordinators/funders will ensure the following:

- Appropriate supply of the study treatments
- Appropriate labeling of all treatments provided that complies with the legal requirements of each country where the study is being performed.

The investigator must ensure the following:

- Indication of appropriately trained blinded site staff (site manager) to manage the drug supply,
 accountability, prescription, administration, and observation.
- Acknowledge receipt of the treatment at the site, including confirmation that the treatments were received in good condition, remained within the appropriate temperature range during shipment

- from production site to the designated storage location, and ensure appropriate storge conditions in accordance with the manufacturer's recommendations.
- Proper storage of treatment: Storage in a secure, locked, temperature-controlled location according
 to the instructions specified on the labels, and appropriate record keeping and inventory, including
 regular documentation of adequate storage temperature.
- Appropriate use of the treatments only in accordance with the approved protocol.
- Complete record keeping of treatment use, wastage, or destruction, including documentation of number of doses destroyed, date of destruction, method of destruction, and name of individual performing destruction.

6.4 Participant Withdrawal Criteria

Other

A participant may discontinue study participation at any time prior to the last planned study visit. This is referred to as premature withdrawal from the study. From the analysis perspective, a 'premature withdrawal' from the study refers to any participant who will not be available for the termination visit foreseen in the protocol (Visit 5). A participant is considered a 'premature withdrawal' from the study when no study procedure has occurred, no follow-up has been performed and no further information has been collected from this participant from the date of premature withdrawal / last contact.

The reasons for premature withdrawal from the study include:

Adverse event

Death

Withdrawal of consent

Lost to follow-up

Administration reason

Protocol deviation

NOTE: Before entering any alternate category as the reason for the participant's discontinuation from the study, the investigator will make every effort to investigate whether safety concerns (adverse event or death) may have been related to the participant's discontinuation from the study. In case of associated safety concerns, this must be described on the Termination electronic Case Report Form (eCRF) page, even if it is not the primary reason for the participant's discontinuation.

Adverse event (AE) as reason for premature study withdrawal:

For any participant withdrawing from study participation prior to Visit 5 (study completion visit), it is important to determine if an AE was associated with the reason for discontinuing the study. This AE must be identified on the eCRF page by indicating "Withdrawn from study due to AE".

Death as reason for premature study withdrawal:

For any participant withdrawn from study participation due to death, this should be noted on the Termination eCRF page and the associated SAE that led to the death must be reported.

Withdrawal of consent as reason for premature study withdrawal:

Participants can withdraw consent for participation in the study at any time without penalty or loss of benefit to which the participant is otherwise entitled.

Reason for early termination will be deemed as "withdrawal of consent" if the participant withdraws from participation due to a non-medical reason (i.e., reason other than AE). If the participant intends to withdraw consent from the study, the investigator will clarify if the participant will withdraw completely from the study or will continue study participation for safety or a subset of other study procedures. If complete withdrawal is specified, no further study interventions will be performed with the participant.

Date of Participant Termination:

The date of termination is the date of the last contact (clinic or home visit or telephone contact) in which the participant's health status was assessed or, in cases where the participant does not agree to any further safety follow-up; it is the date consent is withdrawn.

Lost to follow-up as reason for premature study withdrawal:

For participants who fail to show up for scheduled visits (clinic or home visit), study staff will be expected to make at least three documented attempts to contact the participants and encourage the completion of study termination procedures. These efforts to contact the participants will be recorded in the source documents. The termination date for the participant to be captured on the Termination eCRF page is the date of the last successful visit (clinic or telephone) with the participant.

Administrative reason as reason for premature study withdrawal:

For participants who are withdrawn from the study due to sponsor decision (e.g., meeting, prespecified withdrawal criteria or termination of study by the sponsor), this reason should be noted in the Termination eCRF page and any ongoing AEs at the time of study withdrawal must be followed until resolution/stabilization.

Protocol deviation as reason for premature study withdrawal:

In general, participants associated with protocol deviations may remain in the study unless continuation in the study jeopardizes the participant's health, safety, or rights. For participants who are withdrawn from the study due to receipt of an excluded medication/vaccination or due to significant protocol non-compliance, this reason should be noted in the Termination eCRF page.

Any ongoing AEs at the time of study withdrawal will be followed until resolution/stabilization.

If a participant is withdrawn prematurely from the study for a reason other than those outlined above, this reason must be documented in the Termination eCRF page.

Participants who are withdrawn from study treatment will be encouraged to continue in the study for safety follow-up and other procedures as appropriate until the scheduled termination visit (Visit 5). Withdrawn participant will not be replaced.

The sponsor, coordinator, or the investigator (following consultation with the sponsor) has the right to discontinue this study at any time. If the clinical study is prematurely terminated, the investigator is to promptly inform the study participants and local ethical committee (EC/IRB) and should assure

appropriate therapy and follow up for the participants. All procedures and requirements pertaining to the archiving of study documents should be followed. All other study materials (unused treatments etc.) must be returned to the sponsor.

6.5 Prior and Concomitant therapy

6.5.1 Prior Medications and Vaccines

These include any investigational or non-registered product (drug or vaccine) received prior to enrolment. If these medications were administered to the participant within the specified window period (14 days) prior to treatment, they must be recorded on the Concomitant Medications page of eCRF.

6.2.2 Concomitant Medications and Vaccines

At each study visit, the investigator will ask the participants about any prescription or over-the counter medication(s) taken since the last visit. Any medications taken at any time during the study period must be recorded on source documents and the case report form with trade and/or generic name, indication, dose, start and end dates. Any treatments and/or medications specifically contraindicated, e.g., any investigational or nonregistered product, any antipyretic/analgesic will be checked at each study visit during treatment period. If any became applicable during the study, it would not require withdrawal of the participant from the study but may determine a participant's evaluability in the per protocol analysis.

7.0 ASSESSMENT OF SAFETY

Specification of safety parameters

Safety assessment includes occurrence of solicited systemic adverse reactions (Side or adverse effects), and unsolicited adverse events (AEs), including side effects leading to severe adverse effects and withdrawal, within 35 days after treatment administration.

7.1 Solicited and Unsolicited Safety Measurements

Solicited side adverse effects: The term "side effects" refers to signs and symptoms occurring as unintended clinical effects of the treatment whether or not they are harmful (adverse).

Unsolicited Adverse Events: An adverse event (AE) is any undocumented untoward or unforeseen medical occurrence in a participant or clinical investigation participant administered a pharmaceutical product at any dose that does not necessarily have a known causal relationship with this treatment. This definition includes intercurrent illnesses or injuries and exacerbation of pre-existing conditions. In this study, no severe adverse side effects are expected from the treatment, given that Artemisia herbal teas have been used in communities for malaria prevention with no reported toxicity (29). However, since toxicity is always a major concern in clinical trials involving humans, each study participants will be monitored for adverse side effect or adverse events daily, throughout the study period (within 35 days of treatment administration) and where necessary adequate intervention will be provided. Treatment safety data will be collected continuously by the site staff during site and home visits and recorded in

the predefined visit worksheets at Visit Day 7, 14,28 and 35 (i.e, adverse effects). As a consistent method for collecting unsolicited ASE and AEs in this study, the participant will be asked a non-leading question such as: 'Have you acted differently or felt different in any way since receiving the treatment, or since the last study visit?' Occurrence of any adverse side effects or AEs visit within 35 days of treatment will be assessed by healthcare professional at site or home, meanwhile the site staff will continue contacting the participant daily until effects resolution.

When an AE/ASE occurs, it is the responsibility of the investigator to review all documentation (e.g., hospital records, laboratory, and diagnostics reports) relative to the event. The investigator will then record all relevant information regarding an unsolicited AE/SAE on the eCRF or SAE Report screens as applicable. The investigator will attempt to establish a diagnosis pertaining to the event based on signs, symptoms, and/or other clinical information. In such cases, the diagnosis should be documented as the AE/ASE and not the individual signs/symptoms. The severity of AEs will be determined by the investigator and graded from Mild (Grade 1) to Death (Grade 5) based on the *Division of AIDS (DAIDS) Table for Grading the Severity of Adverse Events* (37).

The relationship of the study treatment to an AE will be determined by the investigator based on the following definitions:

- 1. Not Related: The AE is not related to an investigational treatment if there is evidence that clearly indicates an alternative explanation. If the participant has not received the treatment, the timing of the exposure to the treatment and the onset of the AE are not reasonably related in time, or other facts, evidence or arguments exist that reasonably suggest an alternative explanation, then the AE is not related.
- **2. Related:** The administration of the investigational treatment and AE are considered reasonably related in time and the AE could be explained by exposure to the investigational treatment or by other causes. The relationship of the study treatment to an unsolicited AE will be determined by the investigator.

The causality assessment is made based on the available information at the reporting time point and assessment of causality can change according to follow-up information.

The actions taken in response to an unsolicited AE will be coded as shown below. One or more of these actions may be selected:

- 0 No action taken
- 1 Study treatment temporarily interrupted
- 2 Study treatment permanently discontinued due to this adverse event
- 3 Concomitant medication taken
- 4 non-drug therapy given
- 5 Physician visit
- 6 Hospitalization/prolonged hospitalization

Outcome of any unsolicited AE reported during the study period will be assessed as:
□ Recovered/resolved
☐ Recovering/resolving
☐ Not recovered/not resolved
☐ Recovered with sequelae/resolved with sequelae
☐ Fatal (SAEs only)
Treatment of any AE is at the sole discretion of the investigator and according to current good medical
$practice. \ Any \ medication \ administered \ for \ the \ treatment \ of \ an \ AE \ should \ be \ recorded \ in \ the \ participant's$
eCRF.

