- Proportion of people on the various arms of treatment who develop ASEs or AEs at D7, D14, D28, and D35 from baseline (No severe adverse side effects are expected).
- Proportion of persons on the various arms of treatment who withdraw from study due to severe ASEs or AEs at D7, D14, D28, and D35 from baseline.
- Proportion of persons on the various arms of treatment who withdraw from study for reasons other than severe AEs at D7, D14, D28, and D35 from baseline.
- Proportion of persons with baseline discordant test results (False positive or false negative) between mRDT, rt PCR, and direct blood smear observation?

Exploratory endpoints

- Variability in level of decease in gametocyte load (rt-PCR Ct) in the various treatment arms at D7, D14, D28, and D35 from baseline.
- Variability in level of decease in gametocyte load (rt-PCR Ct) in the various treatment arms by gender, age, and trial entry parasite load, at D7, D14, D28, and D35 from baseline.
- Variability in attainment of absolute increase in Cycle threshold (Ct >20) in the various treatment arms at D7, D14, D28, and D35 from baseline.

- Variability in the proportion of participant who respect and complete prescribed treatment dosages (acceptability) in the various treatment arms.
- Variability in the proportion of participants who develop clinical symptoms in the various treatment arms at D7, D14, D28, and D35 from baseline.
- Variability in the proportion of participants who develop Severe ASEs in the various treatment arms at D7, D14, D28, and D35 from baseline (not expected).
- Variability in proportion of participants who withdraw from the study due to severe ASEs, in the various treatment arms, at D7, D14, D28, and D35 from baseline.
- Variability in proportion of participants who withdraw from the study for reasons other than severe AEs, in the various arms of treatment at D7, D14, D28, and D35 from baseline.

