7.1.1 Serious Adverse Events
A serious adverse event (SAE) is defined as any untoward medical occurrence that at any dose results
in one or more of the following:
- Death.
- Is life-threatening (i.e., the participant was, in the opinion of the investigator, at immediate risk
of death from the event as it occurred); it does not refer to an event which hypothetically might have
caused death if it were more severe.
- Required or prolonged hospitalization.
- Persistent or significant disability/incapacity (i.e., the event causes a substantial disruption of a
person's ability to conduct normal life functions).
- An important and significant medical event that may not be immediately life threatening or resulting
in death or hospitalization but, based upon appropriate medical judgment, may jeopardize the
participant, or may require intervention to prevent one of the other outcomes listed above.
Adverse events which do not fall into these categories are defined as non-serious .
All Severe AEs will be evaluated by the investigator for relationship of the event to study treatment.
The relationship of the study treatment to an SAE will be determined by the investigator based on the
following definitions:
$\hfill \square$ Related/suspected : the SAE is judged by the investigator to be related to the trial treatment ;
$\ \square$ Not Related : the SAE is not related the treatment has not yet been consumed, \mathbf{or} the occurrence of
the SAE is not reasonably related in time, \mathbf{or} the SAE is considered unlikely to be related to use
consumption of the treatment i.e., there are no facts (evidence) or arguments to suggest a causal

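### Section 7.1 limits what counts as an adverse event, names solicited reactions without listing any, and codes only unsolicited events, so mild effects may be under-counted, misfiled or recorded differently between arms

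*Protocol*

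**What the plan says.** Section 7.0 of the protocol sets out two streams of safety data: "Safety assessment includes occurrence of solicited systemic adverse reactions (Side or adverse effects), and unsolicited adverse events (AEs").

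Section 7.1 then defines each stream.
- A solicited side effect is an unintended clinical effect of the treatment, harmful or not.
- For the unsolicited stream, "An adverse event (AE) is any undocumented untoward or unforeseen medical occurrence in a participant". The definition goes on to say that the event "does not necessarily have a known causal relationship with this treatment", and adds: "This definition includes intercurrent illnesses or injuries and exacerbation of pre-existing conditions".

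No solicited reaction is named. The one elicitation tool is introduced this way: "As a consistent method for collecting unsolicited ASE and AEs in this study, the participant will be asked a non-leading question such as", followed by an example of an open question.

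Later in 7.1, severity grading covers adverse events from Grade 1 (mild) upwards. The coding rule is narrower: "The actions taken in response to an unsolicited AE will be coded as shown below". The outcome list is likewise for unsolicited events.

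Section 7.1.1 uses a different base definition: "A serious adverse event (SAE) is defined as any untoward medical occurrence that at any dose" meets one of the listed criteria.

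Section 3 (Clinical symptoms) gives the only symptom list in the protocol. It includes headache, nausea and vomiting, body aches and malaise, labels them mild malaria symptoms, and has them assessed daily and recorded at Days 7, 14, 28 and 35. In Section 2.3.2 the proportion with clinical symptoms is one secondary endpoint, and the safety endpoint is another: "Proportion of people on the various arms of treatment who develop ASEs or AEs at D7, D14, D28, and D35 from baseline". The Synopsis merges clinical symptoms, side effects and adverse events into a single endpoint.

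**The concern.** Safety by concentration, frequency, length and formulation is a secondary objective, and safety and tolerability are part of the hypothesis. Section 7.2 states that there are no safety laboratory measurements, so the safety conclusion rests almost wholly on reported and observed symptoms. The rules for eliciting, classifying and coding symptoms therefore matter more here than in a trial with laboratory safety data.

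Three features weaken those rules. The category an event falls into depends partly on whether the recorder thinks it foreseeable or caused by the tea, although 7.1 elsewhere treats relatedness as a separate judgement that may change with follow-up. The open question is given only as an example, and Section 6.2 assigns one observer to each arm, so any difference in how observers ask or classify is a difference between arms. The same symptom can also count as safety data under one endpoint list and as a malaria symptom under another.

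**Working it through.** The protocol states no expected event rate, capture rate or safety power, so there is no planned figure to reproduce. The main check sets the passages side by side.

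**1. The two definitions do not match.** The adverse event definition in 7.1 carries two limiting adjectives; the serious adverse event definition in 7.1.1 carries neither. Read literally, a serious event could be both foreseen and documented, and so meet 7.1.1 without meeting 7.1.

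**2. Solicited reactions are announced but not specified.** Section 7.0 names them and 7.1 has an entry for them, but no reaction is listed. The only question in 7.1 is labelled as the method for unsolicited events. Nothing links 7.1 to the Section 3 symptom list.

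**3. Coding covers one stream only.** Action and outcome codes are specified for unsolicited adverse events. Side effects, which 7.1 puts in the solicited stream, have no stated action or outcome coding.

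**4. Where a foreseeable mild event ends up:**
- (a) Attributed to the tea: it is a side effect under 7.1 and enters the combined side-effect and adverse-event endpoint.
- (b) Not attributed, but on the Section 3 list (headache, nausea, vomiting, malaise): it is counted as a clinical symptom. That is separate from safety in Section 2.3.2 and pooled with it in the Synopsis.
- (c) Not attributed and not on the list (for example diarrhoea, abdominal pain, dizziness or rash): it is an adverse event if treated as intercurrent illness. Only if it is judged both foreseen and documented does the literal definition leave it without a category.

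So (c) is a narrow gap and (b) is a misfiling problem. Case (a) is counted, though without stated action or outcome codes.

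**5. Consistency between arms.** The definitions are the same in every arm, but their application need not be. There is one observer per arm (Section 6.2), the question wording is not fixed (7.1), and the blinding paragraph of Section 3 says staff know who is in the regular-tea arm (Section 5.5 says they do not). Any distortion could go in either direction.

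**6. Illustration of sensitivity only.** Assume that a fraction c of mild effects is recorded, with c = 1, 0.6 or 0.3, and a true rate of 20%. None of these values comes from the protocol. The arm sizes do: 8 per active arm per site × 2 sites = 16. Three flavoured and three unflavoured active arms give 3 × 16 = 48 on each side.

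The chance that an arm of 16 reports no case is (1 − 0.20c)^16:
- c = 1: 0.80^16 = 0.028
- c = 0.6: 0.88^16 = 0.129
- c = 0.3: 0.94^16 = 0.372

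For flavoured against unflavoured (48 v 48), with assumed true rates of 40% and 20%, the observed gap is (0.40 − 0.20)c = 20, 12 or 6 percentage points. Exact power of a two-sided 5% Fisher test is 0.49, 0.24 or 0.08.

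These figures show how incomplete capture would act at this sample size. They do not estimate the capture the protocol will achieve, and they do not separate the effect of the definition from that of the question.

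**The case against.** A reader might infer that foreseeable mild effects fall into no safety category and that the tea will therefore look safer than it is. The documents do not support either step. The adverse event definition needs no causal link and expressly takes in intercurrent illness and worsening of existing conditions. Effects attributed to the tea are side effects and enter the same endpoint. Grading starts at mild, and 7.1.2 requires follow-up regardless of severity and of association with treatment. Nor does the protocol as a whole solicit nothing: Section 3 has a fixed symptom list assessed daily, and the Synopsis reports it together with side effects and adverse events. This part of the objection stands.

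It can also be said that capture does not rest on one question. There is daily contact, assessment by a healthcare professional when events occur, recording of all medications with their indication, and predefined visit worksheets that are not shown and may contain a checklist. That is fair, and it is one reason the undercount cannot be sized. It does not remove the defects in the text: the limiting adjectives, the solicited category with no content, the codes for one stream only, and two endpoint lists that treat the same symptoms differently.

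A third argument is that 7.1.1 calls adverse events that miss its criteria non-serious, and so treats serious events as a subset of adverse events. That is probably the intention. The definition in 7.1 should then be worded to agree with it.

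**Conclusion.** The point holds as a defect in how the protocol fixes safety collection, and it should be corrected before recruitment. The adverse event definition is too narrow and does not match the serious adverse event definition. Solicited reactions are named without content, action and outcome codes leave out the stream in which tea effects are placed, and symptoms that may be tea effects are counted apart from safety in one place and with it in another. Mild effects may therefore be under-counted, misfiled or recorded differently between arms.

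The size cannot be derived from the documents, and most events will still enter some category. A systematic bias towards safety is a possibility and has not been shown. The capture calculation rests entirely on assumed rates and serves as illustration only.

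**What to change.** 1. In 7.1, define an adverse event as any untoward medical occurrence from informed consent onwards, whether or not it is foreseen, documented or related to treatment. This keeps the observation period in 7.1.2 and makes serious events a subset. Keep pre-treatment events separate, as 7.1.2 already does, and record relatedness as its own item.
2. List a short fixed set of solicited symptoms in 7.1, reconciled with the Section 3 list. State once how symptoms on both lists are counted, so that Section 2.3.2 and the Synopsis agree. Ask the set in the same words in all eight arms at Days 7, 14, 28 and 35, then put the open question.
3. Apply grade, action and outcome codes to solicited and unsolicited events alike.

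The cost is protocol wording and one page on the existing visit worksheet, with no extra visits or blood samples. Reported event rates will rise in all arms, and the report should say that this follows from asking directly.
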